This is not a treatment trial; there is no direct course of therapy related to the participant population being targeted. We are recruiting healthy adults with experience using cannabis and who are not seeking treatment for substance use problems. Should any report the desire for

treatment they will be discontinued and referred to appropriate community service centers. For participants who do not meet full study inclusion/exclusion criteria participation ends after screening procedures. Participants who meet all inclusion/exclusion criteria may also be discontinued if they are unable to complete all inpatient procedures (e.g., are unable to schedule or complete procedures in a timely manner; unable to have an arterial line placed for the PET scan) or where continuation may increase risk as determined by study physicians. Participants will be compensated for their participation in the number of procedures up the point of the premature termination of their participation.

Premature termination of participation may result in the need to recruit additional research volunteers, but should have no impact on the study volunteer directly.

5. Inclusion/Exclusion Criteria

Inclusion criteria.

- Female, healthy adult volunteers who are either MJ users and nonusers (controls)
- 18-45 years of age
- Laboratory parameters within the normal range, unless the Investigator considers an abnormality to be clinically irrelevant for healthy participants; however serum creatinine and hepatic enzymes (AST, ALT) must be within the normal limits/.
- Willing to make themselves available for the duration of the study and are willing to follow study procedures and research unit policies.
- Women of child bearing potential must meet one of the following three criteria:
 - o negative pregnancy test by serum pregnancy test
 - Following a reliable method of birth control (hormonal, intrauterine device, barrier, or abstinence) and
 - agreeing to follow a reliable method of birth control during the study and for one month following all study procedures

Additional inclusion criteria for MJ users

- self-reported MJ use at least 25 days/month for the prior 3 months,
- present MJ positive urine sample at screening and admission,
- meet DSM-5 criteria for moderate to severe CUD
- report at least 2 MJ withdrawal symptoms in previous period of abstinence

Additional inclusion non-users

- report no MJ use in the past 12 months
- Report MJ use of no more than 5 times in lifetime

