- present a MJ-negative urine sample at screening and prior to study procedures.

Exclusion Criteria: Women will be excluded if pregnant, breast feeding, or planning pregnancy; have amenorrhea, or menstrual cycle dysfunction. Other exclusion criteria are:

- 5th grade reading level as determined by the Shipley-2 vocabulary score < 18 or by Rapid Estimate of Adult Literacy in Medicine (REALM Health Literacy Test),
- Current DSM-5 mood or anxiety disorder;
- Current DSM-5 alcohol or substance use disorder (excluding MJ or nicotine)
- Illicit drug use in last 30 days or positive urine test for illicit drugs (excluding MJ for MJ users)
- Using MJ under the guidance of MD;
- History of seizures, closed head trauma;
- BMI <18 or >35;
- Clinically-significant abnormality on ECG;
- unstable hypertension (BP > 150/90);
- conditions preventing MRI (implanted metal, claustrophobia)
- significant anatomical abnormalities on MRI (e.g., enlarged ventricles, brain lesions);
- Use of prescribed medications in last 3 months; over the counter drugs or herbal supplements which may be counter indicated as determined by study physician may also be excluded
- Have had research related exposure to ionizing radiation that in combination with the study's estimated radiation exposure would result in a cumulative exposure that exceeds recommended exposure limits of 5 rem per year.
- Presence or history of drug allergy, or allergic disease diagnosed and treated by a physician.
- any serious medical condition in whom participation is contraindicated.

To determine eligibility, the medical records will be reviewed by study physicians, and psychological assessments and full inclusion/exclusion criteria will be reviewed by Drs. [name] or [name].

6. Drugs/ Substances/ Devices

- a. The rationale for choosing the drug and dose or for choosing the device to be used.
- b. Justification and safety information if FDA approved drugs will be administered for non-FDA approved indications or if doses or routes of administration or participant populations are changed.
- c. Justification and safety information if non-FDA approved drugs without an IND will be administered.

Marijuana (MJ).

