The effects of MJ on an unborn fetus are unknown but are potentially harmful. Women who are pregnant, planning to become pregnant or nursing will be excluded from study participation. Women of child bearing potential must use an effective non-hormonal form of birth control and will have urine pregnancy tests at screening and prior to all procedures; only women with a negative pregnancy test may participate.

PET radiotracer:

¹¹C-OMAR (4-cyano-1-(2,4-dichlorophenyl)-5-(4-methoxyphenyl)-N-(piperidin-1-yl)-1Hpyrazole-3-carboxamide), previously JHU75528, is a CB1R PET radiotracer. It is an analog of the CB1R antagonist/inverse agonist rimonabant. ¹¹C-OMAR was developed, synthesized and first tested in humans at the JHU PET center^(8, 45, 46), and will be used in the proposed studies under IND 76,698 (effective date: 4/20/07), which is held by [name] (Co-I on this protocol). A single dose of approximately 370-1110 MBq of [¹¹C]-OMAR (approximate mass dose of 5 to 14 micrograms) will be administered during the PET scanning procedure by intravenous bolus administration. Each participant will receive a single intravenous injection of [¹¹C]-OMAR.

¹¹C-OMAR is the appropriate radiopharmaceutical for our studies. It has excellent test-retest reproducibility⁽⁹⁾, and has been used successfully and safely in PET studies in alcohol dependent subjects⁽⁵⁶⁾, post-traumatic stress disorder patients⁽⁶¹⁾, schizophrenic patients⁽⁸⁾ and more recently in male cannabis users⁽⁴³⁾.

7. Study Statistics

- a. Primary outcome variable.
- b. Secondary outcome variables.
- c. Statistical plan including sample size justification and interim data analysis.
- d. Early stopping rules.
 - N/A

Derivation of outcome variables. There is no appropriate, reliable reference region for ¹¹C-OMAR due to the widespread distribution of CB1R in human brain. BP_{ND} (non-displaceable binding potential which requires a measure of absolute non-specific binding) is not appropriate for quantification of this radioligand. Volumes of Interest (VOI) will be generated by spatially normalizing⁽⁸³⁾ a standard VOI template⁽⁸⁴⁾ to individual

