- 4. Radiation exposure. A tracer dose of 20 mCi (~740 MBq) is delivered in the PET scan and results in a maximum of 0.227 rem effective dose radiation exposure. From the PET transmission scan, participants receive an additional 0.0026 rem of external radiation exposure. Thus the total radiation exposure from the one PET scan will be about 0.23 rem. If participants are required to have the skull x-rays performed to verify it is safe for the participant to enter the MRI area, the radiation exposure will increase by 0.01 rem. Thus, the total possible maximum amount of radiation exposure from the combined internal and external sources of radiation in this study will be about 0.24 rem, which is below the allowable annual radiation exposure limit of 5 rem per calendar year set by JHU. The amount of radiation exposure is also within the limits set forth by 21CFR361.1.
- 5. Women for child bearing potential: To avoid unknown risks for the fetus, women of child bearing potential must use an effective non-hormonal form of birth control and will have urine pregnancy tests at screening and prior to all procedures; only women with a negative pregnancy test may participate.
- 6. Other risks. Several additional risks occur throughout the course of the PET study. PET risks include a risk of pain, bleeding or infection from the catheters used for PET scan procedures. In rare cases, fainting or infection could occur.

For MJ users only: MJ withdrawal: Abstinence after chronic daily use or near daily use of MJ is associated with MJ withdrawal discomfort that includes increases in anxiety, depression, irritability, anger, sleep problems, and decreased food intake and weight loss⁽³⁴⁻³⁷⁾. In a subset of MJ users, blood pressure can significantly increase during MJ abstinence ⁽⁸⁸⁾. Since this is a focus of the study, and we will be selecting individuals that have shown 2 or more symptoms in the past, it is likely participants will experience some of these symptoms. These symptoms are time delimited, not associated with severe health consequences, and typically resolve on their own within 2 weeks.

Controlled MJ administration.

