MJ is a DEA Schedule I substance. All MJ (active and placebo) will be obtained specifically for use in this study from the Drug Supply System of the National Institute on Drug Abuse (NIDA) and will be stored and dispensed by the BPRU pharmacy. [name] has DEA and Maryland Schedule I Researcher licenses for MJ research. This protocol will be conducted under his DEA license and we are cross-referencing his IND (103,211).

Active MJ will contain MJ (potency approximately 10-13% THC by volume). Placebo MJ contains the plant material from which the THC has been removed via ethanol extraction. A potential risk of smoking MJ is burning or irritation of the throat/lungs. Acute administration of MJ can produce tachycardia, intoxication, altered mood, impaired coordination, and cognitive deficits. Only healthy volunteers who are current MJ users and are fully eligible based on the study inclusion/exclusion criteria will receive MJ. Given the experience of the participants with smoking MJ and the high tolerance to THC demonstrated by prior research participants in our lab, the risk of serious adverse events related to smoking MJ in the laboratory setting is minimal. There is no known risk of overdose or death related to MJ/THC. The effects of MJ on an unborn fetus are unknown but are potentially harmful. Women who are pregnant, planning to become pregnant or breast feeding will be excluded from study participation. Women of childbearing potential must use an effective nonhormonal form of birth control and will have urine pregnancy tests at screening and prior to all procedures; only women with a negative pregnancy test may participate.

Treatment Diversion:

Despite clear efforts to indicate otherwise, participants who are cannabis users may mistake the proposed studies as treatment or may delay treatment seeking in order to participate.

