history and physical exams, with the study physician or the nurse practitioner. Only healthy MJ users may participate in the study. To reduce the risk associated with MJ-induced tachycardia, subjects will have an EKG during the health screen; subjects with a clinically significant ECG abnormality will be excluded. Subjects with uncontrolled hypertension (blood pressure > 150/90) are also excluded from study participation. To further reduce the likelihood of adverse reactions to administration of smoked MJ during the study, nursing staff will be instructed to withhold administration for any participant with heart rate above 120, systolic blood pressure above 160, or diastolic blood pressure above 100. Throughout the MJ administration sessions, subjects are monitored by the research nurse. In case of an emerging or adverse event, the study physician is available via pager for assistance.

Women of child bearing potential and risk to the fetus: The effects of MJ and radiation exposure on an unborn fetus are unknown. Females who are pregnant, planning to become pregnant or nursing will be excluded from study participation. All females must have a negative pregnancy test at screening, prior to CRU admission and prior to study procedures. A positive pregnancy test at any point during the study results in study termination.

Women of child bearing potential must also use a medically acceptable method of contraception for the duration of the study.

Treatment Diversion: All advertisements and the informed consent process will clearly indicate that this research is designated only for those not seeking treatment, that participation is not a substitute for treatment, and that participation offers no clinical benefit. They will be clearly informed that they will be asked to smoke MJ during their participation. Any participant who expresses an interest in receiving immediate treatment for MJ or other substance use will be referred to a community treatment clinic. If this occurs during the study, their participation in the study will be terminated. As previously described, participants will be instructed that should they withdraw from the study at any point to pursue treatment they will still be compensated for their participation up until that point in the study.

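### Section 5 accepts hormonal contraception and, read literally, a negative pregnancy test alone, whereas sections 6 and 8a require non-hormonal contraception together with negative tests

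*Combined protocol and SAP*

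**What the plan says.** Five places in the protocol set contraception rules.

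- **Section 5, inclusion criteria.** The lead-in is "Women of child bearing potential must meet one of the following three criteria". The items are a negative serum pregnancy test, "Following a reliable method of birth control (hormonal, intrauterine device, barrier, or abstinence) and", and an agreement to keep using a reliable method through the study and for a month afterwards.
- **Section 6, Marijuana.** "Women of child bearing potential must use an effective non-hormonal form of birth control". Urine pregnancy tests are added, and a negative result is a condition of taking part.
- **Section 8a, PET and Radiologic Procedures, item 5.** "women of child bearing potential must use an effective non-hormonal form of birth control", with the same testing rule. The stated reason is unknown risk to the fetus.
- **Section 8a, Controlled MJ administration.** "Women of childbearing potential must use an effective nonhormonal form of birth control", again with the same testing rule.
- **Section 8b, risk to the fetus.** "Women of child bearing potential must also use a medically acceptable method of contraception for the duration of the study", in addition to negative tests.

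Two exclusions in section 5 also bear on the point: "Use of prescribed medications in last 3 months", and women who "have amenorrhea, or menstrual cycle dysfunction".

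**The concern.** Section 5 is the list staff use to decide who enters. If it is followed as written, it lets in women whom sections 6 and 8a exclude.

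Two things are at stake. The first is fetal safety: users smoke cannabis and every participant receives radiation, and all are women aged 18 to 45. The second is control of a factor the protocol itself treats as relevant to CB1 receptor availability. The background in section 3 cites steroid-dependent receptor density in rats, section 5 excludes women with disturbed cycles, and section 7 plans to include estrogen and progesterone levels in the V_T analyses. Users and controls are matched on age, race, cigarette use and BMI, not on contraceptive method, with 10 per group. Whether hormonal users may enter should therefore be settled in the eligibility list.

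**Working it through.** No arithmetic applies. No sample size, power or error rate in the plan depends on this rule. The check sets the statements side by side and then tests example cases against them.

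**Step 1. The rules compared**

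| Place | Contraceptive method | Pregnancy test | Duration of contraception |
|---|---|---|---|
| Section 5, inclusion | Any reliable method, hormonal named; not compulsory if another item is met | Serum; one of three alternatives | Study plus one month (third item) |
| Section 6, Marijuana | Non-hormonal, compulsory | Urine, negative, compulsory | Not stated |
| Section 8a, PET item 5 | Non-hormonal, compulsory | Urine, negative, compulsory | Not stated |
| Section 8a, Controlled MJ administration | Non-hormonal, compulsory | Urine, negative, compulsory | Not stated |
| Section 8b | Medically acceptable, compulsory | Negative, compulsory; type not stated | Study only |

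**Step 2. Example cases**

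| Woman | Section 5 inclusion item | Sections 6 and 8a | Section 8b |
|---|---|---|---|
| A: hormonal method, negative tests, agrees to continue | Meets | Fails | Meets, if hormonal methods count as medically acceptable |
| B: negative serum test, no contraception | Meets as worded | Fails | Fails |
| C: barrier method, negative tests, agrees to continue | Meets | Meets | Meets |

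A and B show two separate contradictions. C shows that the rules can all be satisfied together, so the protocol can be carried out. The fault is that the inclusion item is looser than the rest.

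**Step 3. Are the two contradictions independent?** Replacing *one of* with *all of* removes B and leaves A. Deleting the word *hormonal* removes A and leaves B. Section 5 needs both edits.

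**Step 4. Does other text settle the matter?**

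- The bar on prescribed medication would probably exclude many women like A. It does not mention contraceptives, and it pulls against an inclusion item in the same section that names hormonal methods as acceptable.
- Section 5 ends with a review of each volunteer against the full criteria. Those criteria contain the faulty wording, so the review cannot say which rule governs.
- Section 8b does not contradict the non-hormonal rule. It is less specific, and it omits the extra month.

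**Step 5. Side effects of the repair**

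- Once all three items are required, the serum test in section 5 becomes compulsory while sections 6 and 8a speak of urine tests. The text should say which test applies when.
- Section 5 accepts intrauterine devices. If a hormone-free device contains metal (an assumption; the documents do not say), it meets three MRI statements that differ: section 5 lists implanted metal among conditions preventing MRI, section 8a excludes women reporting metal in the body, and section 8b allows implants made of non-magnetic material.

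**The case against.** The strongest reply is that the rules are cumulative and the strictest governs. A woman on a non-hormonal method satisfies every section, and no section other than 5 offers a test-only route. The trailing conjunction suggests that the items were meant to be joined. The three non-hormonal statements are essentially one sentence repeated, so counting them as three decisions against one overstates their weight. Pregnancy is excluded outright and tested for repeatedly. The medication bar, and possibly the cycle exclusion, would remove many hormonal users.

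Most of this stands, and it limits the harm. It does not remove the conflict. Nothing in the protocol says that the strictest rule prevails, and reading the three items as cumulative still leaves hormonal methods expressly permitted. A nested reading (a test, or else a method plus the agreement) would keep the test-only route open.

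It is also fair to object that the documents do not dictate which side should give way. Section 8a justifies the non-hormonal rule by fetal risk. No section says that it protects V_T. The sponsor may intend to allow hormonal methods, and the fix should leave that open.

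A reader might go further and infer that the comparison of V_T between users and controls will be biased by hormonal contraceptive use. The documents do not support this. They give no number of hormonal users, no imbalance between groups and no effect of contraceptives on V_T. Nor do they support an inference that pregnant women would be exposed unnoticed, because negative tests are required before procedures whatever the contraceptive method.

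**Conclusion.** The inconsistency is real and lies in an operative eligibility rule. Section 5 permits a contraceptive method that sections 6 and 8a forbid. On its literal wording it also lets a negative test replace contraception, probably through a drafting slip. The rule could bear on any of the 20 planned participants (10 users plus 10 controls), because the PET statement in section 8a covers everyone scanned.

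The size is modest. Repeated pregnancy testing and the section 5 exclusions limit practical harm, and no effect on V_T is quantified or claimed. The conclusion rests only on the current wording, plus the assumption that a medication bar which does not mention contraceptives cannot be relied on to override an inclusion item that names hormonal methods. It should be corrected because the correction is cheap and removes doubt about both a safety requirement and a hormonal factor that the analysis plan itself brings in.

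**What to change.** Amend the text as follows.

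1. In the section 5 lead-in, require all three items instead of one.
2. In the second item, delete hormonal methods, to match sections 6 and 8a. If the sponsor intends to allow them, amend the three non-hormonal statements and the section 5 medication bar instead, so that all say the same.
3. State that the rule applies to users and controls alike.
4. Specify a serum pregnancy test at screening and urine tests before procedures.
5. Align section 8b with section 5 on the accepted methods and on the additional month.
6. Accept an intrauterine device only if it is non-hormonal and compatible with the metal and MRI rules in sections 5, 8a and 8b.

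The cost is a wording amendment and possibly slightly narrower recruitment, for which the documents give no figure. Visits, sample size and analyses do not change.

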Multiple assessment instruments will be done to determine who should be included and who excluded, and to provide measures that may be included as covariates in analyses. The Mini-International Neuropsychiatric Interview (MINI, v.7)⁽⁶²⁾ for DSM-5 will be used to assess CUD, other SUD, and psychological disorders. Alcohol and MJ use will be characterized using the 90-day Time Line Follow Back (TLFB)⁽⁶³⁾. The MINI and Fagerström Test for Nicotine Dependence (FTND)⁽⁶⁴⁾ will be used to determine presence of tobacco use disorder and severity of nicotine dependence. The Marijuana Quit Questionnaire⁽⁶⁵⁾ and a retrospective Marijuana Withdrawal Checklist (MWC)⁽³⁵⁾ will be used to obtain history of MJ use, quit attempts, and presence of MJ withdrawal symptoms during prior periods of abstinence. Nonusers will be recruited to match MJ users for age, rage, cigarette use and BMI. Only healthy volunteers are eligible. Volunteers who appear eligible for study participation at the end of the screening visit will complete training on the battery of computer assessments, and a screening ECG (see below).

ECG Screening.

The study team physicians with JHBMC privileges will review all health information to determine initial study eligibility. Any participants with a history of heart disease, or blood pressure that exceeds a systolic blood pressure of 150 mmHg or a diastolic blood pressure of 90 mmHg will be excluded. Only healthy volunteers are eligible. Although cannabinoids in general do not have an ECG indicated for their prescription, a 12-lead ECG will be conducted in those that appear to meet all other study inclusion/exclusion criteria as an additional screening procedure. If the ECG shows any abnormalities, a credentialed cardiologist will determine if the abnormality may be clinically significant (incidental findings). Participants that have clinically relevant ECG abnormalities will be excluded from further study participation.

Outpatient Session 1

Cannabis users and Controls who meet eligibility criteria will come to the BPRU for and complete an MRI in the morning. In the afternoon, Controls will complete the cognitive performance tasks, and MJ users will complete an outpatient session that includes cannabis self-administration and cognitive performance tasks (see below).

MRI Procedures.

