Eligible participants will have a MRI scan of the head to identify the anatomy of the brain for coregistration with the PET images. The MRI exam will take approximately 40 min. Prior to the MRI, each participant will be asked to complete a standard questionnaire to determine if the participant has any metal in the eyes or head. The purpose of this questionnaire is to ensure that the participants are safely able to enter the MRI area. After answering this questionnaire, a small number of participants may be required to undergo two anteriorposterior (AP) skull x-rays to further determine if it is safe for them to enter the MRI area. If the skull x-rays are necessary, the MRI staff will explain the x-ray procedure to the participant. The results of the x-rays will then determine if it is safe for the participant to enter the MRI area. An extremely small number of participants are determined to be unsafe to enter the MRI area based on the questionnaire and/or xrays. If this should happen, or if the participant chooses not to have the x-rays, the participant will be removed from the study.

Clinical Research Unit (CRU) Stay

MJ users will complete a 4-day protocol that includes a stay on the Bayview CRU for 3 nights. MJ users will complete procedures as part of an inpatient stay. Throughout the CRU stay participants can use a telephone, have reading material and watch television. No visitors will be allowed during the CRU stay. Throughout the CRU stay, cannabis users will complete daily assessments three times daily (7am, noon, 7pm). Assessments include:

- Vital signs (heart rate, blood pressure)
- Breath CO levels
- Profile of Mood State (POMS) ^(66, 67)
- Beck Anxiety Inventory (BAI)⁽⁶⁸⁾
- Marijuana Withdrawal Checklist (MWC) ⁽³⁵⁾
- Marijuana Craving Questionnaire Short Form (MCQ-SF)⁽⁶⁹⁾.

Laboratory assessment of MJ withdrawal.

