subjects on Spoiled Grass (SPGR) sequenced MRI volumes. VOIs are: ventral striatum, amygdala, putamen, cingulate, globus pallidus, insula, frontal cortex, and hippocampus to target regions associated with drug reward, mood, cognition, motor function and habit learning (see Aims). V_T will be obtained for each VOI by plasma reference graphical analysis (PRGA); we have previously demonstrated that PRGA showed more robust estimates of V_T than the two-compartment model, as measured with time dependency of estimates and the magnitude of inter-subject variability⁽⁸⁾. V_T is a standard outcome for many receptor binding radiopharmaceuticals.

Sample size and Power Analysis: We propose a use of 10 subjects per group (total n=20) to reliably detect CB1R differences in MJ users vs. controls. We completed power analyses with SAS v3.2.2 using our mean and SD ¹¹C-OMAR V_T data, and assuming equal variance per group, we have 95% power for amygdala and globus pallidus, and 80-89% power for putamen, cingulate, insula, frontal cortex, and hippocampus to detect a significant (p<0.05) group difference in V_T of 10% or greater. We will be underpowered to detect 10% change for the ventral striatum (63% power, p<0.05), but this VOI is not one of those hypothesized to be downregulated in withdrawal. Thus, we have sufficient power (\geq 80%, p<0.05) for our study aims.

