Statistical Analysis Plan: Baseline participant characteristics will be summarized and compared between groups (female MJ users vs. controls). For each outcome variable descriptive statistics will be generated; continuous variables will be reported as means (SD) and categorical variables as frequencies and percentages. Outcome variables will undergo data cleansing and evaluated for accuracy and missing data. We will perform exploratory data analyses (stem-leaf displays, box plots, histograms, and Q-Q plots), and, if necessary, appropriate data transformations will be performed. Groups will be matched for age, race, BMI and nicotine use, and we will use propensity score analysis⁽⁸⁵⁾ to evaluate group differences. To compare the groups across different VOIs, we will use a general linear model, where V_T will be the dependent variable with group status (encoded as a dummy variable) as the independent variable, along with covariates for age, race or any other variables indicated by propensity analyses. All VOI-based statistical analyses will be done with SPSS (IBM) statistical software. After the initial VOI-based analyses, we will also use Statistical Parametric Mapping (SPM)^(83, 86) to identify changes of V_T across groups without restrictions of VOIs. The same linear models used in VOI-based analyses will be applied to the voxel-based analyses. We plan to use a threshold level of p = 0.05, FDR-corrected, and the minimal cluster size at 50 voxels (~0.4 ml). Using the SPM package for MATlab, our model will also include fixed and random effects⁽⁸⁷⁾.

Aim 1: To examine the relationship between V_T and severity of CUD, our model will have V_T as the dependent variable, and severity of CUD (number of symptoms on the MINI) as the independent variables.

Aim 2: To determine if VT will be associated with greater withdrawal severity, greater craving and increased negative mood during cannabis abstinence, our model will have V_T as the dependent variable, and assessment instrument scores for mood and MJ withdrawal (MWC)⁽³⁵⁾ and craving (MCQ-SF)⁽⁶⁹⁾ as the independent variables (Hypothesis 2).

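### The plan states no partial-volume correction or grey-matter term for V_T, so a group difference in regional tissue share, if there is one, could be read in part as CB1R downregulation

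*Combined protocol and SAP*

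**What the plan says.** Section 7, Derivation of outcome variables, builds the regions from a standard template: "Volumes of Interest (VOI) will be generated by spatially normalizing" it to individual "subjects on Spoiled Grass (SPGR) sequenced MRI volumes". The outcome follows directly: "V_T will be obtained for each VOI by plasma reference graphical analysis (PRGA"). No tissue segmentation, grey-matter mask or partial-volume step is mentioned.

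Both groups have the structural scan. Section 4, Outpatient Session 1: "Cannabis users and Controls who meet eligibility criteria will come to the BPRU for and complete an MRI in the morning". Its stated purpose, under MRI Procedures, is anatomical: "Eligible participants will have a MRI scan of the head to identify the anatomy of the brain for coregistration with the PET images". Its only other stated use is exclusion, in section 5, for "significant anatomical abnormalities on MRI (e.g., enlarged ventricles, brain lesions").

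The group model in the Statistical Analysis Plan has group status "along with covariates for age, race or any other variables indicated by propensity analyses". The Exploratory Aim paragraph adds estrogen and progesterone levels for V_T. The SPM step inherits this: "The same linear models used in VOI-based analyses will be applied to the voxel-based analyses". None of these names a grey-matter measure.

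Hypothesis 1 in section 2 predicts lower V_T in users and calls the difference downregulation.

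**The concern.** V_T in a PET region depends on receptor density and on what tissue the region holds. A template region fitted to a brain still contains some white matter and CSF, and PET blurring mixes signal across its edges. If users have a smaller grey-matter share in a VOI than controls, their measured V_T would be lower with no change in receptors. A larger share would hide a true loss.

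The comparison is not randomised and each participant has one scan, so neither design nor repetition removes an anatomical difference. The target effect is a 10% difference in V_T, so a bias of a few percent would be a visible part of it. The result would be read as a receptor finding, while the data that could test the alternative are collected and not used for that purpose.

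**Working it through.** **Inputs from the plan.** 10 per group; a 10% difference in V_T; p<0.05; stated power of 95% (amygdala, globus pallidus), 80-89% (five VOIs) and 63% (ventral striatum), all in section 7, Sample size and Power Analysis. Sidedness is not stated; two-sided is assumed here.

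**The plan's own figure.** The stated power cannot be reproduced, because no regional mean or SD of V_T is given. It can be inverted. For a two-sample t test with 18 degrees of freedom, critical value 2.101 and non-centrality d × √(10/2), the d that gives each stated power, and CV = 10%/d, are:

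| Stated power | d | Implied CV |
|---|---|---|
| 95% | 1.706 | 5.86% |
| 89% | 1.508 | 6.63% |
| 80% | 1.325 | 7.55% |
| 63% | 1.083 | 9.23% |

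**Assumptions, not in the documents.** Grey-matter share of a VOI f = 0.70 to 0.85; V_T of non-grey tissue as a fraction r of grey = 0.25 to 0.50; users' share lower than controls' by a relative gap of 2%, 5% or 8%; no receptor difference.

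**Tissue model.** Measured V_T = V_GM × [f + (1 − f)r]. A relative gap e in f changes measured V_T by e × k, where k = f(1 − r) / [f + (1 − f)r].

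- f = 0.70, r = 0.50: k = 0.350/0.850 = 0.412
- f = 0.85, r = 0.50: k = 0.425/0.925 = 0.459
- f = 0.70, r = 0.25: k = 0.525/0.775 = 0.677
- f = 0.85, r = 0.25: k = 0.6375/0.8875 = 0.718

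One case in full: f = 0.70, r = 0.50, e = 5%. Controls measure 0.70 + 0.30 × 0.5 = 0.850. Users, with f = 0.665, measure 0.665 + 0.335 × 0.5 = 0.8325. The ratio is 0.979, so V_T is 2.1% lower. Then d = 2.06/7.55 = 0.27, non-centrality 0.61, and the chance of p<0.05 is 9%.

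**Results at CV 7.55%**, over the four combinations of f and r:

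| Relative gap in share | Spurious V_T difference (e × k) | d | Chance of p<0.05 |
|---|---|---|---|
| 0% | 0 | 0 | 5% |
| 2% | 0.8-1.4% | 0.11-0.19 | 6-7% |
| 5% | 2.1-3.6% | 0.27-0.48 | 9-17% |
| 8% | 3.3-5.7% | 0.44-0.76 | 15-36% |

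The same calculation at CV 5.86% gives 6-8%, 12-25% and 22-55%. At CV 9.23% it gives 5-6%, 8-13% and 12-26%.

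**Limits.** The test is unadjusted, whereas the plan's model has covariates. Only tissue fraction is modelled; spill-over is not quantified.

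**The case against.** The strongest objection is that harm needs a group difference in grey-matter share, and the documents offer no evidence of one, in women or in men. That stands: the table shows what could happen, not a demonstrated bias. The plan also has partial safeguards: individual normalisation of the template, matching on age, race, BMI and nicotine use, ages 18-45 only, and exclusion of enlarged ventricles and lesions. The propensity wording could admit a further covariate. These lower the risk, but none measures or names grey matter.

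A second objection is that the document is a short protocol form that cites outside papers for PRGA, normalisation and the template. A reader might infer that no correction is done. The documents support only that none is stated.

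Three stronger readings are tempting and also fail:

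- *Much higher error rates.* With r = 0 the spurious difference equals the gap itself, and the rates at CV 7.55% become 9%, 29% and 61%. That requires non-grey tissue to contribute no V_T at all. It fits poorly with a total distribution volume and with section 7's statement that CB1R are too widespread to allow a reference region.
- *Lost power.* A reader might infer that tissue variation adds noise the sample size did not allow for. Power was computed from the team's own observed V_T data. If those data were processed the same way, the scatter is already in the SD.
- *Distorted Aim 1 and Aim 2 associations.* These are within users, so bias would require tissue share to track symptom severity or withdrawal scores. The documents say nothing on that.

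**Conclusion.** The point holds as a conditional one. The plan states no partial-volume correction, segmentation or grey-matter term for V_T, although a structural MRI is planned for every participant in both groups, and it interprets lower V_T as receptor loss. A modest gap in grey-matter share (5% relative) would by itself produce about a fifth to a third of the 10% target effect (2.1/10 to 3.6/10). These sizes rest on assumed tissue fractions, an assumed non-grey signal and a CV inferred from the stated power. A reader might conclude that the planned comparison is biased, or that a lower V_T in users would be a tissue artefact. The documents do not support either. They support only that the alternative explanation is left unexamined when it could be checked cheaply.

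**What to change.** In section 7, Statistical Analysis Plan:

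1. State whether any partial-volume correction is already applied, and keep uncorrected V_T as the main outcome.
2. Segment the SPGR MRI already acquired and report grey-matter fraction per VOI by group.
3. Prespecify one sensitivity analysis: repeat the group V_T model with partial-volume-corrected V_T, by a single named method. Report both estimates with confidence intervals side by side.
4. Fix in advance how much shrinkage counts as material. Where the two estimates disagree in direction, or the difference shrinks by more than that, state that the V_T difference cannot be attributed to CB1R alone.

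Naming one method matters: with 20 participants and eight VOIs, a choice between methods made after seeing the results would carry little weight. A sensitivity analysis is preferable to another covariate in so small a main model.

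The cost is analyst time, with no new scan, visit or radiation. Corrected V_T will be noisier, so its intervals will be wider. This is a low-priority improvement.
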